1.0 Objectives / Specific Aims

The objective of this study is to determine the safety and efficacy of 24-hours vs. 72-hours continuous infusion of octreotide after successful endoscopic treatment of esophageal varices and overt gastrointestinal bleeding.

2.0 Background

Esophageal variceal hemorrhage due to portal hypertension is a dreaded clinical complication in patients with cirrhosis and is associated with significant morbidity and mortality.¹ It is usually managed with pharmacologic, endoscopic, and radiological techniques, and sometimes surgery.¹ The current standard of care includes intravenous infusion of the somatostatin analogue, octreotide, which is usually started as soon as variceal hemorrhage is suspected, followed by urgent or emergent endoscopy, and treatment typically with band ligation (EBL) within 8 to 24 hours.^{1,2} Intravenous octreotide is then continued for three, and up to five days, although currently available guidelines are not clear on the appropriate duration of therapy.

The rational for using octreotide is that it reduces portal blood flow, which reduces portal pressure, and hence reduces the propensity for variceal bleeding. The pharmacology of octreotide suggests that the benefits are transient due to desensitization and/or tachyphylaxis.³ The appropriate duration of continuous octreotide infusion is uncertain and largely based on expert opinion. Prolonged infusion of octreotide is thus likely to be unnecessary, and may inappropriately increase hospital and medical costs.

In randomized-controlled trials, the duration of vasoactive drugs has varied between 8-hours and 6-days.^{4,5} Most studies that show benefits of octreotide in decreasing recurrent variceal bleeding compared octreotide with other vasoactive agents, such as vasopressin and terlipressin.⁶⁻⁸ A few also compared octreotide with endoscopic sclerotherapy. The standard of care for bleeding esophageal varices is octreotide and EBL. However, the role of continuing octreotide after successful EBL is unclear. One pharmaceutical-sponsored randomized trial in 1995 showed that the relative risk (RR) of rebleeding was lower in patients when octreotide infusion was continued for 5-days after EBL compared to patients with EBL alone (RR=0.22).⁹ In this study, however, octreotide was not given prior to endoscopy, which is now part of the standard-of-care. A second pharmaceutical-sponsored multicenter, randomized, double-blind study compared vaptoreotide (another synthetic somatostatin analogue) to placebo in patients with suspected esophageal or gastric variceal bleeding.^{10,11} Patients were randomized to receive vaptoreotide or placebo at the time of presentation and the treatment was continued for 5-days after endoscopic treatment (sclerotherapy or band ligation). Control of bleeding and survival was significantly better on vaptoreotide (compared to placebo) at the time of endoscopy (69% vs. 54%), at 48-hours (73% vs. 54%), and at Day 5 (66% vs 50%). There was no difference in recurrent bleeding after 3 days, duration of hospitalization, or mortality. Notably, the difference in bleeding and survival occurred within the first 6-hours of vaptoreotide infusion vs. placebo, and then became non-significant suggesting that the effect occurs early on.

In a recent randomized-controlled trial, patients were started on octreotide infusion before endoscopic therapy (band ligation or sclerotherapy) and then octreotide was continued for 2-days vs. 5-days.⁵ Two days of octreotide infusion were found to be as efficacious as the 5-days of infusion in preventing early rebleed, suggesting that prolonged infusion of octreotide may be unnecessary.

The above studies suggest that octreotide infusion for longer than 24 hours may be clinically unnecessary, which also raises the issue of the expense of continuing the medication. Hence we propose a randomized study to determine whether shortening the length of time of octreotide after endoscopic band ligation affects the rate of variceal rebleeding.

3.0 Intervention to be studied (if applicable)

The study will be a prospective, randomized-controlled multi-center study.

- Patients with overt, or active, variceal bleeding will be randomized to octreotide infusion for either 24-hours or 72-hours following successful endoscopic band ligation (EBL).

4.0 Study Endpoints (if applicable)

Primary Endpoint:

- Rebleeding within 72-hours after control of hemostasis with EBL

Secondary Endpoints:

- Rebleeding within 7 and 30-days
- Survival within 7 and 30-days
- Complications from octreotide, including, but not limited to: pneumonia, cardiac complications (arrhythmias, heart failure, cardiac ischemia), paralytic ileus, hyperglycemia, diarrhea, abdominal pain, nausea

Rebleeding within 72-hours will be defined as any of the following:

- A drop in hemoglobin by more than 20 percentage points from baseline
- Sustained tachycardia above 100 beats per minute, with or without hematochezia or melena
- Transfusion of >2 unites packed red blood cells after EBP
- Recurrence of hematemesis or ongoing melena
- Urgent or emergent need for Transjugular Intrahepatic Portosystemic Shunt (TIPS)." to control suspected rebleeding

Rebleeding after 72-hours will be defined as:

- Any new episode of hematemesis, melena, or hematochezia (with hemodynamic instability)
- Drop in hemoglobin by more than 20 percentage points OR the need for >2 units packed red blood cells
- Need for TIPS or surgery to control suspected bleeding

Patients who rebleed will be treated per hospital standard of care and physician preference. Treatment of rebleeding will be recorded.

Follow-up Endpoints:

Thirty, 60, 90, 180-day, and 1-year follow-up.

Rebleeding after 72-hours will be defined as:

- Any new episode of hematemesis, melena, or hematochezia (with hemodynamic instability)
- Drop in hemoglobin by 20 percentage points OR need for >2 units packed red blood cells
- Need for TIPS or surgery to control suspected bleeding

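### Any single item makes a 72-hour rebleed, and two items (ongoing melena, tachycardia with no bleeding sign) need not begin after banding, so persisting signs of the index bleed count as primary events

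*Combined protocol and SAP*

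**What the plan says.** Protocol section 4.0 gives the primary endpoint as "Rebleeding within 72-hours after control of hemostasis with EBL". The item list opens with "Rebleeding within 72-hours will be defined as any of the following", so one item is enough. The items that matter here are:

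- "Sustained tachycardia above 100 beats per minute, with or without hematochezia or melena"
- "Recurrence of hematemesis or ongoing melena"
- "A drop in hemoglobin by more than 20 percentage points from baseline"
- "Transfusion of >2 unites packed red blood cells after EBP"
- urgent or emergent TIPS, which alone is tied to its purpose: "to control suspected rebleeding"

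For events after 72 hours, the same section asks for a new episode of overt bleeding and has no stand-alone tachycardia item.

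In section 5.0, melena is an entry sign in its own right (criterion 2a). Tachycardia appears only in the alternative route 2b, where it must exceed 155 beats per minute and accompany both hypotension and fresh rectal bleeding. Sections 3.0 and 10.0 place randomization after successful EBL.

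**The concern.** The endpoint's title promises bleeding that returns after hemostasis, but the item list does not carry that condition through. Ongoing melena describes something that has not stopped. The tachycardia item needs no bleeding sign and gives no time of onset. A patient who came in with melena, was banded successfully and still passes melena the next day meets the primary endpoint as written. The hemoglobin baseline is undated; if it is the presenting value, a fall caused by the index bleed can also count. The transfusion item is dated after banding but not tied to suspected new bleeding, so replacing index blood loss can meet it; this is a lesser point.

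Two things are at stake in a non-inferiority trial. Events unrelated to treatment raise the observed rate and its variance, which costs power when the durations are equal. Events shared by both arms also shrink a true difference, which moves the comparison toward non-inferiority when the shorter infusion is worse.

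**Working it through.** **Inputs from section 11.0 (Statistical Analysis) and section 6.0.** Primary hemostasis rate 90%, margin 15 points, 90% power, type I error 0.05, 69 per group, about 15% drop-out, rebleeding rates of 10-30%, total 160 (80 per group).

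**Inferred or assumed.** The 10% control risk is read from the 90% hemostasis rate. The one-sided level is inferred from the sample size. A claim of non-inferiority means that the upper one-sided 95% limit for the risk difference lies below 15 points. The share *f* of patients without true rebleeding who still meet an item is not in the documents and is varied.

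**1. The plan's own figure.** n = 2 × 0.9 × 0.1 × (1.645 + 1.282)² / 0.15² = 68.5, so 69 per group. One-sided 0.025 would give 85. The stated figure therefore reproduces at one-sided 0.05.

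**2. Model.** With true risk p, the observed risk is q = p + (1 − p)f. A true excess of 15 points is observed as 15(1 − f) points. The chance of claiming non-inferiority is

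P = Φ( [0.15 − (qT − qC)] / √{[qC(1 − qC) + qT(1 − qT)]/n} − 1.645 ).

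Power sets both true risks at 10%. The false-claim rate sets them at 10% and 25%, exactly at the margin.

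**3. Worked case, f = 5%, n = 69.**
- Power: q = 0.10 + 0.90 × 0.05 = 0.145; standard error √(2 × 0.145 × 0.855/69) = 0.0599; Φ(0.15/0.0599 − 1.645) = 0.80.
- False claim: qT = 0.25 + 0.75 × 0.05 = 0.2875; observed difference 0.1425; standard error 0.0690; Φ(0.0075/0.0690 − 1.645) = 0.062.

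**4. Results at 10% control risk.**

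| f | Observed control risk | Power, 69/group | Power, 80/group | False claim, 69/group | False claim, 80/group |
|---|---|---|---|---|---|
| 0 | 10.0% | 90% | 94% | 5.0% | 5.0% |
| 2% | 11.8% | 86% | 90% | 5.5% | 5.5% |
| 5% | 14.5% | 80% | 85% | 6.2% | 6.3% |
| 10% | 19.0% | 73% | 78% | 7.5% | 7.7% |
| 20% | 28.0% | 62% | 68% | 10.2% | 10.7% |

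Exact binomial probabilities at 69 per group agree to within 0.6 of a point. In patients, f = 5% is 69 × 0.9 × 0.05 = 3.1 false events per arm when the true risk is 10%; f = 10% is 6.2.

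**5. Higher control risks, 69 per group, f = 0, 5%, 10%.**
- Control risk 20%: power 71%, 66%, 62%; false claims 5.0%, 6.1%, 7.2%.
- Control risk 30%: power 61%, 59%, 57%; false claims 5.0%, 6.0%, 7.1%.

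The false-claim effect hardly depends on the inferred 10%. The power lost to carry-over is largest there; at 20-30% most of the shortfall comes from the control risk itself.

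**6. The opposite error.** If a stricter definition removes all carry-over but detects only 90% of true rebleeds in both arms, the observed risks are 9.0% and 22.5% at the margin. With 69 per group the false-claim rate is then 8.1%, and power 92%. On the false-claim rate alone, removing carry-over of 5% or 10% pays only if sensitivity stays above about 95% or 92%.

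**The case against.** **The broad early definition may be intended.** The trial is sized on primary hemostasis, so failure to hold hemostasis is arguably part of what is counted, and the authors asked for a new episode only after 72 hours. This stands as a reason to call it a design choice. It also confirms that early signs need not be new, and it does not fit an endpoint titled as rebleeding after hemostasis. Reading recurrence as governing melena too does not help: a recurrence of something ongoing contradicts itself, and the tachycardia item raises the problem without it.

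**Tachycardia is not a general entry sign.** A reader might infer that melena and tachycardia are equally carried over from entry. Section 5.0 does not support that: patients entering by 2a need no tachycardia, and 2b uses a different level with further conditions. Only melena is a stand-alone entry sign.

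**The power loss may be smaller.** The 72-hour endpoint falls while all patients are to be in hospital (section 10.0), so much of the planned drop-out need not affect it. That stands, and is why the 80-per-group figures are shown.

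**The false-claim figures need an assumption.** They apply the margin to true rebleeding. If it applies to the endpoint as defined, the nominal 5% is unchanged. Section 11.0 does not settle this.

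**A strict new-or-worse rule can lose real events.** Melena that persists because bleeding truly continues would drop out. That stands, and the fix allows for it.

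**Conclusion.** The point holds. As written, persisting signs of the index bleed are primary events; this is a stated rule that misclassifies, not just missing detail. Its size is unknown because the documents do not say how often melena or tachycardia persists after EBL. If 5-10% of patients without rebleeding meet an item at 10% control risk, power falls from 90% to 80-73% with 69 per group, or from 94% to 85-78% with 80. The false-claim rate rises from 5% to roughly 6-7.5%, provided that the margin is meant for true rebleeding. Up to f = 5% the false-claim effect is small.

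Two stronger conclusions might be inferred and are not supported. The first is that the definition favors one arm: randomization follows EBL, so carry-over should be balanced in expectation. The second is that tightening the definition must lower the false-claim rate: this depends on *f* and on the sensitivity of the new rule, and the documents give neither.

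**What to change.** 1. Reconcile the item list with the endpoint's title. State that melena and tachycardia already present at EBL do not count on their own unless they are new or worse than a recorded post-EBL reference, or the investigator judges that bleeding is continuing. The investigators set the thresholds and decide whether tachycardia alone is enough.
2. Date the hemoglobin baseline to a post-EBL value, and say whether the fall is a per cent of that value.
3. Record the reason for each transfusion, so that replacement of index blood loss can be told apart from treatment of suspected new bleeding.
4. Report the current any-item definition as a sensitivity analysis.

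**Cost.** Protocol wording and a few form fields: timed post-EBL heart rate, stool and hemoglobin, and the transfusion reason. No case report form is in the documents, so some may already exist, and patients are already to be monitored in hospital for at least 72 hours. Treatment, sample size and follow-up do not change. The downside is that a stricter definition may miss some true rebleeds, which is why the clause on continuing bleeding and the sensitivity analysis are included. That clause adds judgment, so its basis should be recorded for each case.

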10.0 Study Design / Methods

This prospective and randomized controlled trial will involve administration of either octreotide infusion for 24-hours (Group A) or for 72-hours (Group B). This study involve the following:

Screening

Esophageal varices as the sole cause of upper gastrointestinal (GI) bleeding will need to be confirmed. Endoscopic band ligation will be performed per standard of care when deemed appropriate by the treating physician.

During this time, and regardless of participation in the research study, octreotide will be administered per standard-of-care before endoscopy. Endoscopy with band ligation will be performed per standard-of-care, if needed. Not all patients may have variceal bleeding and even if varices are present, not all may need EBL. Only patients who receive EBL for varices with stigmata of bleeding will be randomized for the study, to receive octreotide infusion for 24- or 72-hours after successful EBL. Subsequent care will be per the primary team and not affected by participation in the study.

Treatment:

Randomization will be conducted for all enrolled subjects at all site by the study coordinator and coinvestigators at MUSC. Only after undergoing EBL will patients be randomized by computer-generated blocked randomization for treatment allocation. The randomization schedule will be blinded in sequentially numbered opaque envelopes.

Patients will be randomized to receive octreotide as a continuous intravenous infusion for 24-hours or 72-hours after the infusion is started. Following standard-of-care for variceal bleeding, all patients will be monitored in the hospital for at least 72-hours after undergoing esophagogastroduodenoscopy (EGD) and EBL. Any recurrent bleeding will be managed per standard-of-care, which may include a combination of octreotide infusion, placement of an esophageal balloon tamponade tube (i.e. Minnesota tube, or similar), repeat endoscopic intervention, referral to Interventional Radiology for transjugular intrahepatic portacaval shunt (TIPS), or surgery.

Follow-Up:

The follow-up of this study will take place until 1-year after the initial bleeding episode and information will be collected via chart reviews of the medical records and follow-up phone calls at: 30-days, 60-days, 90-days, 180-days, and 1-year after the initial visit. Phone calls will take

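### Surgery to control bleeding, and hematochezia with hemodynamic instability, count as rebleeding after 72 hours but not in the primary 72-hour definition, so a narrow type of true rebleed can be scored as no event

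*Combined protocol and SAP*

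**What the plan says.** Section 4.0 makes the primary endpoint "Rebleeding within 72-hours after control of hemostasis with EBL". The definition is a composite in which one item is enough ("Rebleeding within 72-hours will be defined as any of the following"). It has five items:

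- a hemoglobin fall of over 20 percentage points relative to the starting value
- the heart-rate item: "Sustained tachycardia above 100 beats per minute, with or without hematochezia or melena"
- over 2 units of red cells given once banding is done
- recurrent hematemesis or melena that continues
- the procedure item, which applies when rebleeding is suspected: "Urgent or emergent need for Transjugular Intrahepatic Portosystemic Shunt (TIPS"

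The definition for rebleeding after 72 hours, printed twice in the same section, differs. Its procedure item is "Need for TIPS or surgery to control suspected bleeding". Its bleeding item covers new hematemesis, new melena, and hematochezia accompanied by hemodynamic instability.

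Section 10.0 (Treatment) describes how recurrent bleeding may be managed. Besides octreotide, TIPS and surgery it names "placement of an esophageal balloon tamponade tube (i.e. Minnesota tube, or similar), repeat endoscopic intervention". Section 4.0 adds that the treatment given for rebleeding is recorded, but nothing links that record to the endpoint.

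Section 11.0 states the design: non-inferiority, a 15% margin, a 90% primary hemostasis rate, 69 per group for 90% power, and type I error 0.05.

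**The concern.** Two definitions of the same event should differ across a time boundary only for a stated reason, and none is given here. As written, surgery for suspected bleeding is an event on day 4 and not on day 2. Hematochezia with hypotension is an event on day 4, but on day 2 only if the heart rate also stays above 100. In the 72-hour list the mention of hematochezia adds nothing, because sustained tachycardia qualifies with or without it, and hypotension is not named at all.

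The mismatch falls on the primary endpoint of a non-inferiority trial. If true rebleeds are missed at the same rate in both groups, the observed difference shrinks in proportion while the margin stays fixed. The error therefore helps the 24-hour group to pass.

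**Working it through.** **Step 1. The two lists side by side (Section 4.0).**

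| Feature | Within 72 h (primary) | After 72 h |
|---|---|---|
| Hematemesis, melena | counts | counts |
| Hematochezia with instability | only if sustained rate above 100 | counts |
| Sustained rate above 100 alone | counts | not listed |
| Hemoglobin drop, or more than 2 units | counts | counts |
| TIPS | counts if urgent or emergent | counts |
| Surgery | not listed | counts |
| Repeat endoscopic hemostasis, balloon tamponade | not listed | not listed |

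Two rows lose events within 72 hours relative to the later list: hematochezia with instability, and surgery. The last row is the same on both sides of the boundary.

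**Step 2. One patient through both lists.** Take hematochezia, hypotension, heart rate 92, no hematemesis or melena, 2 units given, a hemoglobin drop that does not pass the threshold, and repeat banding. At hour 40 the five items read no, no, no (2 is not more than 2), no, no, so the result is no rebleeding. At hour 80 the hematochezia item is met, so the result is rebleeding. This assumes that one item suffices in the later list too. Replacing the banding with surgery does not change the hour-40 result.

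**Step 3. The plan's own sample size.** Inputs from Section 11.0: 90% in both groups, margin 0.15, power 90%. With one-sided alpha 0.05:

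n = (1.645 + 1.282)² × (0.9×0.1 + 0.9×0.1) / 0.15² = 8.564 × 0.18 / 0.0225 = 68.5, rounded up to 69.

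This matches the plan. One-sided 0.025 would give 85, so the test is taken as one-sided 5%. The plan's 80 follows as 69 × 1.15 = 79.35, rounded up.

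**Step 4. Effect of missed rebleeds.** Assumptions:
- The 90% success rate is read as 10% true rebleeding in the 72-hour group.
- The 24-hour group sits exactly at the margin, at 25%.
- The list catches a share s of true rebleeds, equally in both groups, with no false positives.
- The documents do not give s, so a range is shown.

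Observed rates: pA = 0.25s and pB = 0.10s, so the observed difference is 0.15s.

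SE = √[pA(1−pA)/n + pB(1−pB)/n]

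P(declare non-inferiority) = Φ[(0.15 − 0.15s)/SE − 1.645]

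Example with s = 0.95 and n = 69: pA = 0.2375, pB = 0.095, difference 0.1425, SE = 0.0622. Then (0.15 − 0.1425)/0.0622 = 0.121, and Φ(0.121 − 1.645) = 6.4%.

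| True rebleeds missed | Observed difference (points) | n = 69 per group | n = 80 per group |
|---|---|---|---|
| 0% | 15.0 | 5.0% | 5.0% |
| 1% | 14.85 | 5.3% | 5.3% |
| 2% | 14.7 | 5.5% | 5.6% |
| 3% | 14.55 | 5.8% | 5.9% |
| 5% | 14.25 | 6.4% | 6.5% |
| 10% | 13.5 | 8.1% | 8.4% |
| 20% | 12.0 | 12.9% | 13.8% |

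Exact binomial enumeration at n = 69, using the same Wald bound, gives 5.4% with nothing missed and 6.9%, 8.8% and 14.2% at 5%, 10% and 20% missed. The normal approximation therefore runs slightly low.

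**The case against.** The strongest reply is that the composite is broad. A rebleed escapes only if every item is negative. Sustained tachycardia alone, hematemesis, continuing melena, more than 2 units or a hemoglobin drop will catch most bleeds serious enough to need rescue. This stands, and it is why the low end of the range is the plausible one. A reader might infer that the list misses the clearest clinical failures. The documents do not support that: a bleed needing surgery or tamponade will usually meet another item.

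A second reply is that Section 10.0 describes management and is not a competing definition. This also stands. A reader might take the absence of repeat endoscopy and balloon tamponade from the 72-hour list as a contradiction with Section 10.0. It is not: treatments for an event need not be criteria for it, and both are missing from the later list as well. Nor is TIPS the only treatment-based item, since transfusion is another.

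Third, entry criterion 2b in Section 5.0 accepts bright red blood per rectum only with both hypotension and tachycardia, so tying hematochezia to heart rate has a precedent in the protocol. That softens the criticism, but it does not explain why the requirement for tachycardia disappears after 72 hours.

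Fourth, beta-blockers might blunt the heart rate, but Section 10.0 names them only under follow-up (medications during admission are recorded in general terms). How many patients take them during the first 72 hours is unknown.

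Finally, over-counting may be the larger error, since tachycardia alone or melena that merely continues can count without a new bleed. With an assumed 5-10% false-positive rate among patients who do not rebleed, power at 69 per group falls from 90% to about 81-73% (exact enumeration). That is a separate problem and does not recover missed rebleeds.

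**Conclusion.** The two definitions in Section 4.0 are inconsistent on surgery and on hematochezia with instability, and the primary 72-hour rule can score a true rebleed as a non-event. The route is narrow: hematochezia with hypotension and every listed item negative. With 1-5% of true rebleeds missed equally in both groups, false non-inferiority at the margin is about 5.3-6.4% against a nominal 5% with 69 per group.

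A reader might take the 8-13% figures as the expected harm. They require 10-20% of true rebleeds to miss every item, and nothing in the documents suggests a share that large. All these figures rest on assumed miss rates, true rates of 25% and 10%, equal misses in both groups and no false positives. The lists should be reconciled because the correction is cheap and concerns the primary endpoint, not because the non-inferiority conclusion is shown to be in serious danger.

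**What to change.** In Section 4.0, bring the 72-hour list into line with the later one:

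1. Add surgery to the TIPS item.
2. Add hematochezia with hemodynamic instability as an item of its own, and define instability for the endpoint, since the documents do not.

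Preferably, also count repeat endoscopic hemostasis or balloon tamponade actually performed for suspected rebleeding, in both lists. This is an improvement rather than a correction. Its drawback is that the decision to re-intervene is discretionary and made by staff who know the allocation, as is already true of TIPS and transfusion.

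The cost is about two lines of text and tick-boxes on the rebleeding form, since treatment of rebleeding is already recorded. Only what is counted changes, not how anyone is treated. Possible over-counting from tachycardia alone or continuing melena is left untouched and needs separate attention.
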